The testing session is expected to take 45 to 60 minutes, depending upon the attention span and cooperation of the child; this includes regular breaks and relaxation points. It will not be possible to blind the researcher as to which group test participants have been allocated, as those patients with strabismic amblyopia will likely be easily identified due to the presence of their strabismus.

Background information will be recorded on data collection sheets (Appendix 1), and results of the vision tests are recorded as data files on the experimental/display computer. Participants need only complete one testing session, but may complete to 3 sessions over the 24 month period. Additional sessions would allow for analysis change over time. Participants

are free to decide on the length of their participation and can leave the study at any time.

Background information

Prior to testing, the following relevant clinical information will be taken from the patient's digital medical records, or measured and recorded by the PI who is a registered Orthoptist;

- 1. Age
- 2. Gender
- 3. Diagnosis and Amblyopia subtype
- 4. Identification of fellow and amblyopic eye
- Most recent SLT visual acuity result for each eye, for healthy volunteers this will be assessed by the PI.
- 6. Current refractive correction
- Stereoacuity measurement. For healthy volunteers this will be assessed by the PI to ensure inclusion criteria are met.

This information will be used to identify which group the participant will be recruited to (anisometropic, strabismic or control) and also to aid randomisation of initial testing eye within each group. The participant will also be allocated a participant number and all results will be recorded using this participant number to preserve anonymity.

Randomisation

Each group will undergo covariate adaptive randomisation using minimisation to select which eye will be examined first (Hu et al., 2014). Test participants will have either their Amblyopic eye (AE) or Fellow eye (FE) assessed first for all 3 experiments, and control participants will have either their Right eye (RE) or Left eye (LE) assessed first. This will ensure equal distribution of known confounding variables (e.g. amblyopia density, occlusion regime, gender) for testing order bias between eyes. This minimisation process will allow for better statistical analysis and extrapolation of results. The order of experiments will be counterbalanced to prevent testing order bias.

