It will not be possible to guarantee equal distribution within groups across age, as it is expected that most recruited participants will be around 5 years of age because the National Vision Screening programme occurs during the first year of school.

Materials

The presentation and control of visual stimuli will use custom-written Matlab programmes (MathWorks[™], Natick, USA), using the 'Psychophysics Toolbox Version 3 (PTB-3)' on a 15"MacBook Pro with Retina Display, operating an Intel HD 630 Graphics card. The monitor will be calibrated and gamma corrected using an OptiCal photometer (Cambridge Research Systems). This will secure a linear progression of luminances, ensuring the input selected matches the luminance output produced, allowing for correct interpretation of the results. The screen resolution will be set to the highest possible spatial resolution (1920x1200 pixels)

16

and the frame rate will be set to the highest frame rate compatible with the aforementioned spatial resolution.

Optotypes for the 'Enhanced Cambridge Crowding Test', 'Contrast-modulated Cambridge Crowding Test' and the 'Crowding Distance Test' will each be printed onto respective matching cards, allowing for participants to point to what they see, if they are unable or unwilling to name the displayed visual stimuli.

Methodology

All participants will have the tests explained to them in the form of an astronaut story and they will complete tasks (the 3 modified vision tests) in order to help the astronaut complete his/her missions successfully. This will ensure that the examination is fun and engaging, with the aim of improving compliance and concentration. The eye not being tested will be occluded with an eye patch, or a patch that clings to a spectacle lens. All assessments will be completed at 3m, as this will allow the researcher to sit near the child so they can encourage compliance. Amblyopic eyes may be moved closer to the screen to accommodate for their poorer vision, and their threshold scores recalculated accordingly.

Staircase procedures will be used to measure vision (Lalor, 2018; Pelli, Waugh, Martelli *et al*, 2016; Waugh *et al.*, 2018). The staircase is a quick, efficient and popular method of determining an accurate visual acuity threshold; it is therefore an appropriate method of evaluating visual acuity thresholds with young children in clinical settings (Cornsweet, 1962; Corwin, Kintz and Beaty, 1979; Witton, Talcott and Henning, 2017).

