Following completion of the vision tests, participants will be asked if they wish to be involved again with the study. If they do, then they will be tested again following their next Orthoptic review with the ACPOS clinic, or at a time that suits the family best. If they do not, this is the end of their participation.

Consideration of measurement tools, validity and reliability

The results will be generalizable to the entire UK screening population of 3 to 11-year-olds, due to the use of a control group, ensuring external validity.

Participant bias will be controlled and intra-observer reliability maximised using the rigorous set of forced-choice psychophysical testing procedures described above and a single specialized researcher. The researcher is a qualified clinical Orthoptist with many year's experience working with children in vision screening clinics, ensuring that the results will be obtained as accurately and consistently as possible. Test/re-test reliability is ensured by the use of randomization of the order in which the eyes are examined, and counterbalancing the order of the experiments.

Statistical consideration and Data management and analysis

Anonymised data from the 3 experiments will be stored digitally on the experimental computer, which is password protected and only accessible to members of the research team. Data will be compiled in an Excel spreadsheet, ready for analysis.

The data will be analysed using SPSS or Statistica with Repeated Measures Analysis of Variance models. Visual acuities, crowding and critical spacing estimates will be compared between normal and amblyopic groups. Confirmation of normality and sphericity will be assessed with a Shapiro-Wilk test and Mauchley's Test of Sphericity and where necessary, error rates will be adjusted with a Huynd-Feldt Correction in order to ensure that type 1 errors (incorrect rejection of the null hypothesis) are less likely. The rate of improvement of visual acuity, crowding and critical spacing over the treatment period will also be compared (in those participants who opt to complete more than one assessment session) between the three modified tests, and the SLT.

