A Bland-Altmann analysis will also be used to assess levels of agreement between the different test measures, rather than examination of correlation alone. This is because while a high correlation may be an interesting finding, it does not necessarily indicate agreement between the different test measures (Martin Bland and Altman, 1986).

Study Setting

The study will take place in a first floor clinical room with daylight fluorescent lighting, within the University Eye Clinic on [name], Cambridge; and will take place Monday to Friday, 9am to 5pm.

Clinic Address:

University Eye Clinic,

[name],

Cambridge,

[name]

[contact]

Site	Activities
ACPOS clinic - based at the University Eye	Patient Identification point
Clinic	Potential participants approached and
	given study information leaflets by ACPOS
	clinician.
Experimental/clinical room – based at the	Recruitment, consent, recording of
University Eye Clinic	background information, completion of
	visual acuity testing.

The study room is a modified clinical room. It contains appropriate seating for a participant to be tested as well as sufficient and comfortable space for the presence of the researcher and the participant's parent/guardian. Bathrooms are located on the same corridor, and access to the first floor is available via stairs or a lift. Telephones are present within the testing room and additional staff are present in the building at all times the clinic is open, ensuring that help can be obtained at all times should an unexpected emergency arise. University firstaid is available directly using the phone in the testing room. The clinical suitability of these rooms for the purposes of visual acuity assessment has been evaluated by Anglia Ruskin University and an appropriate risk assessment has been completed.

Sample and Recruitment

Study population and sampling technique:

This study will prospectively examine children who fail vision screenings at school and those already being treated. Amblyopic and control participants (aged 3 to 11 years) will be identified via ACPOS (Addenbrooke's Community Paediatric Ophthalmology Service) hosted by the University Eye Clinic. The ACPOS clinic will be a Patient Identification Centre (PIC), and an information poster will be present in the ACPOS waiting room to alert patients that they may be asked if they would like to participate (Appendix 1).

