Potential participants will have been identified by ACPOS clinicians as having anisometropic or strabismic amblyopia. Control participants of similar age will also be recruited via the ACPOS clinic as false positive referrals from the screening service. Healthy volunteers will also be acceptable as control participants. The pool of amblyopes projected for 18 months is n=278; 60% strabismic, n=167 (based on a 2016-2017 Addenbrookes audit).

As the participants will mostly have undertaken the normal screening programme and be following treatment plans as guided by the Royal College of Ophthalmology, these results should be able to be generalised to all UK 3 to 11-year-olds diagnosed with amblyopia.

Eligibility Criteria – Inclusion criteria:

- **Test participants;** Male and female 3 to 11-year-old children diagnosed by ACPOS clinicians as likely having amblyopia (strabismic or anisometropic). They will be tested following 6 weeks (or more) of refractive adaption.
- Control Participants; Male and female 3 to 11-year-old children who have been falsely referred into the Hospital Eye Service (ACPOS) by the visual screening service, or healthy volunteers who have satisfactory visual functions, as per the national screening guidelines.
- All participants must be able to complete the Sonsken logMAR Test (SLT) either verbally or via use of a matching card.

Eligibility Criteria – Exclusion criteria:

- Uncorrected refractive error.
- The presence of any other vision limiting medical condition, not listed in the inclusion criteria.
- Any prior or existing medical history of epilepsy or seizures.

Sample Size:

Based on data produced from previous studies, the outcome data obtained from this study will come from an underlying continuous and normal distribution.

As the first alternative hypothesis is two-tailed, a t-test is appropriate for the calculation of sample size, to find an estimated effect size, with standard deviations known for the visual acuity measures (Hulley and Cummings, 1988). A comparison of means during statistical analysis (Repeated Measures ANOVA) makes this a suitable strategy for determining sample size.

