The effect size is set at 0.100 logMAR, which is the minimum inter-ocular difference that should exist for the participant to be classified as amblyopic (Elliott and Firth, 2009). The standard deviation of the visual acuity measure is set as ± 0.100 logMAR. In adults, visual acuity repeatability measures of ± 0.1 logMAR have been found (Klein et al, 1983; Arditii & Cagenello, 1993; Siderov & Tiu, 1999). Lalor (2018), who used staircase procedures like those proposed, found for children aged 3 to 16 years, standard deviations of ± 0.06 logMAR. Pilot studies with the Crowding Distance Test have suggested even lower standard deviations of the test measures (Waugh et al., 2018).

Using a standardarised effect size of 1 (effect size/sd of measure; or Cohen's d of 1), a significance level or probability of committing a type 1 error (incorrect rejection of null hypothesis), of 0.05; and the probability of committing a type 2 error (incorrect acceptance of null hypothesis) of 0.2 (power of 0.8), a sample size of n=16 participants in each group

30

(amblyopes and control participants) will be required to achieve statistical significance, if a difference exists.

In brief, the data generated will be analysed using a Repeated Measures Analysis of Variance (with Huyndh-Feldt correction for violation of sphericity of variance). In this procedure means are compared. Also post-hoc Tukey comparisons between groups can be made; or a Dunnett test comparing each group (anisometropic; strabismic) to the control group (normal controls)

The above calculation is sufficient for a comparison of means. The second hypothesis involves three distinct groups with independence of observation. An alternative way to estimate sample size is to conduct a one-way ANOVA using an effect size *Cohen's f*, is set at 0.4 (for "large" effect size) to examine for large effect sizes. Once again, the significance level or probability of committing a type 1 error is set at 0.05, and the probability of committing a type 2 error is set at 0.2, to yield a study power of 80%.

Following this power calculation, a sample size of n=21 participants in each group (anisometropic amblyopes, strabismic amblyopes and control participants) will be required to achieve statistical significance, if a difference exists.

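### Comparisons of raw thresholds between amblyopic and control children carry no age term, although groups are formed by diagnosis, ages run from 3 to 11, and no age-matching rule is given.

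*Combined protocol and SAP*

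**What the plan says.** Under Statistical consideration and Data management and analysis, the plan uses repeated measures ANOVA and states that "Visual acuities, crowding and critical spacing estimates will be compared between normal and amblyopic groups". The Sample Size section restates that model and adds Tukey comparisons, or Dunnett comparisons of each amblyopic subtype with controls. The list of steps after the Hypotheses adds a comparison with existing data from healthy children; Patient & Public Involvement puts that earlier sample at 200. None of these places names age as a covariate, factor or stratum.

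On how the groups arise and how age is handled:

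- Background information: the child's group (anisometropic, strabismic or control) follows from the clinical record. Age is the first item recorded.
- Randomisation: minimisation chooses only which eye is tested first, within each group. Its stated aim is "equal distribution of known confounding variables (e.g. amblyopia density, occlusion regime, gender) for testing order bias between eyes"; age is not among the examples. The section ends by saying "It will not be possible to guarantee equal distribution within groups across age", because "it is expected that most recruited participants will be around 5 years of age".
- Study population and sampling technique: "This study will prospectively examine children who fail vision screenings at school and those already being treated". For controls, "Control participants of similar age will also be recruited via the ACPOS clinic", and then "Healthy volunteers will also be acceptable as control participants", with no age condition on volunteers beyond the 3 to 11 range.

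**The concern.** Diagnosis, not randomisation, separates the groups, so nothing in the design balances age between them. The recruitment routes differ. Amblyopic children may already be in treatment, and so may be older than children newly referred from screening. Controls are false-positive referrals or volunteers. The stated intention that clinic controls be of similar age has no band, ratio or procedure.

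If thresholds change with age over this range, an unadjusted contrast estimates the effect of amblyopia plus slope x age gap. Two consequences follow.

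- Where there is no true difference (a fellow-eye v control contrast, say), the false-positive rate rises above 5%.
- Where a difference exists by selection (amblyopic-eye acuity v controls), its size is biased and its confidence interval covers too seldom.

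If the age slope differs by test, the bias differs by test as well, which matters in a study meant to compare tests.

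The point is limited to raw thresholds. An additive age effect shared by the two eyes cancels in an inter-ocular difference. H1 as worded, and H2 if read as inter-ocular difference, are therefore not exposed. The Sample Size section does size H1 as amblyopes v controls; if that contrast is run on raw thresholds, it is exposed too.

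**Working it through.** **The plan's own sample sizes.** These are not in dispute.

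- H1, difference 0.100, SD 0.100, two-sided 0.05, power 80%: n = 2(1.96 + 0.84)² x (0.100/0.100)² = 15.7, so 16 per group, as stated. The exact t-test needs 17; power at 16 is 78.1%.
- H2, three groups, f = 0.4: N = 63.3. The stated 63 gives 79.8% power.

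**Inputs for the effect of omitting age.** The residual SD of 0.10 logMAR and the group sizes (21 per group; 42 amblyopes pooled; 200 existing children) come from the documents. The within-group age SD (1.5 years), the slope (0.01 to 0.03 logMAR per year) and the gap in mean age (1 to 2 years) are assumptions.

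**Formula.** With no true group difference:

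- bias b = slope x gap
- total SD s = √(0.10² + (slope x 1.5)²)
- SE = s√(1/n₁ + 1/n₂)
- the rejection rate is that of a noncentral t with n₁ + n₂ − 2 df and noncentrality b/SE.

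**Worked case**, slope 0.03, gap 1 year, 21 v 21: b = 0.03; s = √(0.01 + 0.045²) = 0.1097; SE = 0.1097 x √(2/21) = 0.0338; noncentrality 0.887; critical t on 40 df 2.021; rejection rate 13.9%.

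| Slope x gap | Bias (logMAR) | 21 v 21 | 42 v 21 | 42 v 200 |
|---|---|---|---|---|
| 0.01 x 1 | 0.01 | 6.1% | 6.5% | 8.9% |
| 0.02 x 1 | 0.02 | 9.3% | 10.9% | 20.3% |
| 0.03 x 1 | 0.03 | 13.9% | 17.2% | 36.2% |
| 0.03 x 2 | 0.06 | 40.9% | 52.2% | 89% |

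Simulation (40,000 runs; 10,000 for 42 v 200) agrees within half a point. With age fitted, the simulated rate is 4.8% to 5.2% throughout. A group comparison of inter-ocular difference stays at 5.0% to 5.1% without the age term.

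**Ages clustered near 5.** Suppose controls and new amblyopes have mean age 5 and SD 0.5, and a share f of amblyopes is already in treatment, with ages uniform from 5 to 9 (mean 7). The gap is 2f years. For slopes 0.01, 0.02 and 0.03 at 21 v 21:

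- f = 0.25, gap 0.5 year: 5.3%, 6.1%, 7.5%
- f = 0.5, gap 1 year: 6.1%, 9.5%, 15.0%

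**When a difference exists.** For a true 0.10 logMAR deficit, with older amblyopes and acuity improving with age, the mean estimate is 0.10 − b: 0.09, 0.07 or 0.04 for b = 0.01, 0.03 or 0.06. Simulated coverage of the 95% interval is 94%, 86% or 59%. If amblyopes are younger, the estimates are 0.11, 0.13 or 0.16.

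**Power cost of fitting age**, 0.10 logMAR at 21 v 21. Unadjusted power is 88.5%. The variance of the adjusted contrast is inflated by 1 + gap²/((2/21) x 40 x 1.5²) = 1 + gap²/8.57.

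| Gap (years) | Inflation | Power, formula | Power, simulated with random ages |
|---|---|---|---|
| 0 | 1.00 | 88.5% | 87.7% |
| 1 | 1.12 | 84.9% | 84.0% |
| 2 | 1.47 | 74.2% | 73.4% |

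These figures credit age with no explained variance. If the slope is 0.03 and the total SD is 0.10, the residual SD is √(0.01 − 0.045²) = 0.089, and power at a 2-year gap is 82-83%.

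**The case against.** The best counter-case has five parts.

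- **The age sentence under Randomisation speaks of balance within groups**, in a section about which eye is tested first. It may not concern a gap between amblyopes and controls at all. That reading is fair. The concern survives it, because it rests on grouping by diagnosis, separate recruitment routes and the absence of any age term or matching rule.
- **The main questions are about inter-ocular difference.** This stands and limits the point. So does a related one: if crowding is scored as crowded minus isolated acuity, an additive age effect common to both cancels there too. The documents do not say how it is scored. An age effect that is the same on every test would fall on the group main effect, not on group x test.
- **The false-positive examples are not explicit plans.** No fellow-eye v control contrast is spelled out, and treated children could fall in either subtype, so a subtype age gap has no stated cause. For amblyopic-eye acuity, bias and coverage are the relevant measures.
- **The high rates need a steep slope and a wide gap.** The 41%, 52% and 89% figures require 0.03 per year and 2 years, against an expectation of ages near 5 and similar-aged controls. The Sample Size section cites an SD of 0.06 logMAR in children aged 3 to 16. If that is a between-child SD and ages were uniform (SD 13/√12 = 3.75 years), the slope could not exceed 0.06/3.75 = 0.016. At slopes of 0.01 to 0.016 and gaps of 0.5 to 1 year, the 21 v 21 rate is 5-8% with SD 0.10 and 6-13% with SD 0.06. The cited SD may instead be repeatability, so this ceiling is not firm, but it favours the lower half of the range. The 42 v 200 figures also assume a gap from children whose ages are not reported.
- **Adjustment costs power if ages differ.** True, and quantified above. The higher unadjusted power in that case belongs to a biased contrast.

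**Conclusion.** The concern holds for between-group comparisons of raw thresholds and for the comparison with the existing healthy children. The plan has no age term and no operational age-matching rule, so following it as written can mix age with diagnosis. The size cannot be fixed from the documents. Under the assumptions shown, false-positive rates at 21 v 21 run from about 5% (ages clustered near 5, shallow slope) to 41% (0.03 logMAR per year, 2-year gap), and the lower part of that range is the more plausible on the protocol's own expectations. For amblyopic-eye acuity the bias is 0.01 to 0.06 logMAR on a design difference of 0.10. H1 as worded is not threatened. The change is worth making because it costs little and because adjustment chosen after seeing the data would be harder to defend.

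**What to change.** Prespecify age (continuous, centred) and age x test as covariates in every between-group model of raw thresholds. Apply the same adjustment to the comparison with the 200 existing children if their ages were recorded. Report age by group. State which analyses use single-eye thresholds and which use differences; comparisons of inter-ocular difference need no age term for an effect common to both eyes.

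This changes analysis wording only, since age is already collected. The cost is under 0.1 point of power if mean ages are equal, about 1 point averaged over chance imbalance, and more if a real gap appears: at 2 years, power is 73-75%, below the planned 80%, unless age explains variance. Two things would offset that. If the existing children's ages are available and a common slope is assumed, fitting them in the same model gives 87-89% for the new tests at a 2-year gap. A stated age-frequency-matching rule covering both clinic controls and volunteers would narrow the gap itself, at some cost to recruitment.

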Finally, crowding distance, the spatial distance over which crowding occurs, in normal foveal (central) vision is small (2-4 arcmin) and cannot be measured with current standard clinical optotypes due to their large size (5 arcmin for 0.0 logMAR acuity) (Danilova and Bondarko, 2007; Huurneman et al., 2012; Siderov, Waugh and Bedell, 2013; Pelli et al., 2016). To get around this difficulty, a new vision test was recently created to quantify the crowding distance or "critical spacing" of crowding (Pelli, Waugh, Martelli et al., 2016). It uses a new "Pelli" font (see Figure 3), which is much thinner horizontally than standard clinical fonts, allowing the optotypes to get closer to each other in physical space. This 'Crowding Distance Test' permits quantification of the critical spacing of crowding for the first time in a clinical population. The new "Pelli" font, each optotype appearing like tall skinny numbers, has already been trialled on 'visually normal' school-aged children (Waugh et al., 2018), but not yet examined on children with greater sensitivity to visual crowding, i.e., amblyopes. The third vision test in the proposed research, will investigate whether or not "crowding distance" measures made in each eye, results in greater inter-ocular differences, leading to better detection of anisometropic and strabismic amblyopia than does the current clinical standard visual acuity test, the Sonksen logMAR test (SLT).

8

Figure 3: 'Pelli' font

By using closer first-order target optotypes, second-order target optotypes, and quantifying crowding distance in paediatric populations, the ability to detect amblyopia and monitor amblyopia treatment, could be significantly improved for the first time since the 1960s. At that time crowding was first quantified in a clinical population of adult amblyopes (Flom, Weymouth and Kahneman, 1963) and was subsequently incorporated into commercially available tests as best practice.

THEORETICAL FRAMEWORK

Clinical Appointment with clinical vision test (SLT) Identification and recruitment of amblyopic and control particpants

Vision tested with modified vision tests

Analysis of results

Research questions and aims

Research question:

"Do the new vision test modifications offer better sensitivity to detection of inter-ocular difference leading to improved detection and monitoring of amblyopia, than the Sonksen logMAR test (SLT)?

Secondary research question:

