"Is there a difference in sensitivities of these modifications to detecting strabismic amblyopia versus anisometropic amblyopia?"

Hypotheses

Null hypothesis 1 (H1₀): The new crowding tests do not offer better sensitivity to inter-ocular differences in acuity in amblyopic children, than the Sonksen logMAR test (SLT).

Alternative hypothesis 1 (H1_a): The new crowding tests do offer better sensitivity to interocular differences in acuity in amblyopic children, than the Sonksen logMAR test (SLT).

Null hypothesis 2 (H2₀): There is no difference in the sensitivities of the new tests to detecting strabismic amblyopia, versus anisometropic amblyopia.

Alternative hypothesis 2 (H2_a): There is a difference in the sensitivities of the new tests to detecting strabismic amblyopia, versus anisometropic amblyopia.

The following steps will be taken in order to complete this project:

- 1. Critically appraise relevant literature about the effects of crowding on visual acuity in normal and amblyopic adults and children for first-order and second-order optotypes.
- 2. Design a study to incorporate three suggested modifications to current visual acuity and crowding tests, in a sample of child control and amblyopic participants.
- 3. Statistically analyse the results, comparing those obtained on control and amblyopic children, as well as with data already gathered from normal healthy children. Data from the new tests will be compared with each other and with those obtained using the standard clinical vision test (the Sonksen logMAR Test: SLT).
- Accept or reject the given null hypotheses and discuss impact on clinical practice in a written thesis, as well as disseminate results at scientific conferences and in scientific peer-reviewed journals.

Study design, methods of data collection and data analysis

Study design

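### The analysis plan does not specify a test of Hypothesis 1: no stated analysis contrasts the inter-ocular difference on a new test with that on the SLT

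*Combined protocol and SAP*

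**What the plan says.** Under Hypotheses, the first alternative reads "The new crowding tests do offer better sensitivity to interocular differences in acuity in amblyopic children, than the Sonksen logMAR test (SLT". Its subject is the difference between the two eyes, its population is amblyopic children, and its comparator is the SLT.

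The section Statistical consideration and Data management and analysis names four things:

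- The model: "The data will be analysed using SPSS or Statistica with Repeated Measures Analysis of Variance models". The repeated factors are not named.
- The cross-sectional comparison: "Visual acuities, crowding and critical spacing estimates will be compared between normal and amblyopic groups".
- Change over time, in children who choose to return: "The rate of improvement of visual acuity, crowding and critical spacing over the treatment period will also be compared" between the three modified tests and the SLT.
- Agreement: "A Bland-Altmann analysis will also be used to assess levels of agreement between the different test measures".

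Sample Size adds follow-up tests: "Also post-hoc Tukey comparisons between groups can be made; or a Dunnett test comparing each group" with the control group. It also sets the number for Hypothesis 1 at 16 amblyopes and 16 controls.

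The intended comparison appears outside the statistical section. The numbered steps under Hypotheses say "Data from the new tests will be compared with each other and with those obtained using the standard clinical vision test". The Rationale asks whether the contrast-modulated test and the crowding distance measure give larger differences between the eyes, in each case with the SLT as the standard. Crowding distance itself is described only in minutes of arc: "in normal foveal (central) vision is small (2-4 arcmin".

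**The concern.** Hypothesis 1 is a within-child question: does the gap between amblyopic and fellow eye grow when the child moves from the SLT to a new test? Where the plan links this hypothesis to a procedure, in the sample size and the group comparisons, that procedure compares amblyopes with controls. Amblyopes enter the study because their acuity is reduced, so they should differ from controls on any reasonable acuity test, the SLT included. A significant group difference on a new test could then be reported as support for Hypothesis 1 without the gain over the SLT ever being estimated.

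The other two analyses do not fill the gap. Rate of improvement concerns change, in a self-selected subset. Bland-Altman is applied to test measures and not to IODs. On thresholds, its bias is a shift between tests, and the Rationale itself says second-order targets are crowded more in normal vision too, so such a shift can occur with no gain in IOD.

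There is a second gap. No analysis scale is set for crowding distance, which is a spacing, whereas the SLT result is in logMAR.

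**Working it through.** **Inputs from Sample Size:** effect 0.100 logMAR, SD 0.100 logMAR (0.06 also quoted from a study in children), two-sided alpha 0.05, power 0.80, and 21 per group, hence 42 amblyopes and 21 controls.

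**1. The plan's own figure.** n per group = 2 × (1.96 + 0.84)² × (0.1/0.1)² = 15.7, so 16. The figure reproduces as a two-sample comparison of amblyopes with controls. (The exact t calculation gives 17; power at 16 is 78.1%.) It is not a calculation for a within-child contrast of IODs.

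**2. What the group comparison can show.** With 42 versus 21, a deficit of 0.1 and SD 0.1, the noncentrality is 1 × √(42 × 21/63) = 3.74 on 61 df, giving power of 95.7%. For a deficit of 0.3 it is about 100%.

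A simulation of 4,000 runs shows how little this bears on Hypothesis 1. It assumed a mean SLT IOD of 0.2, measurement SD 0.1, and the same gain for every child. Percentage of runs significant:

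| Analysis | No IOD gain | Gain 0.1 logMAR |
|---|---|---|
| Amblyopic eye v control eye, new test | 99.8 | 100 |
| Group-by-test interaction, one eye | 4.5 | 74.8 |
| IOD(new) − IOD(SLT), amblyopes | 5.0 | 88.4 |

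**3. Precision of the contrast that answers Hypothesis 1.** Let C = (AE − FE) on the new test minus (AE − FE) on the SLT, where AE and FE are the amblyopic and fellow eyes. With four independent errors of SD s, SD(C) = 2s.

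- s = 0.06: SD(C) = 0.12; SE = 0.12/√42 = 0.019; detectable gain = 2.80 × SE = 0.05 logMAR.
- s = 0.10: SD(C) = 0.20; SE = 0.20/√42 = 0.031; detectable gain = 0.09 logMAR.

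At s = 0.10, power for a 0.10 gain is 88.6% with 42 children, 76.8% at alpha/3 for three new tests, and 58.7% in one subtype of 21. For a 0.05 gain with 42 it is 35%.

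These figures count measurement error only. If the true gain varied between children with SD 0.15 (assumed), SD(C) would be √(0.12² + 0.15²) = 0.19 to √(0.20² + 0.15²) = 0.25, and the detectable gain about 0.08 to 0.11 logMAR.

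**4. Scale of crowding distance.** Assume spacing doubles from 3 arcmin in the fellow eye to 6 in the amblyopic eye. The IOD is 3.0 in arcmin, 3/60 = 0.05 in degrees, and log10(2) = 0.30 in log units. Against an assumed SLT IOD of 0.25 logMAR, these read as 12 times larger, 5 times smaller, and 1.2 times larger. Across fellow-eye values of 2 to 4 arcmin the same doubling is 2 to 4 arcmin but always 0.30 log units.

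**The case against.** A reader might infer that the plan cannot test Hypothesis 1 and never compares tests. The documents do not support that. The repeated factors are unstated, not ruled out. Mauchly's test and the Huynh-Feldt correction matter only for a within-child factor with at least three levels. Repeat sessions are optional, so test is a natural candidate, though session, with up to three visits, is possible. Both eyes are measured on every test, so an eye-by-test or group-by-test term is available, and the simulation shows that a group-by-test term responds to a gain. Bland-Altman is a between-test analysis, and the synopsis, the Rationale and the numbered steps record the intent to compare with the SLT. All of this stands. It shows that the aim is documented; it does not supply a pre-specified test, and the one procedure tied to Hypothesis 1 by number is amblyopes versus controls.

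A reader might also infer that the crowding distance result will depend on the unit. That holds only if a linear spacing difference is set against a logMAR difference, which no section proposes. The section on computer generation of stimuli allows a logMAR score, and Sample Size sets Crowding Distance Test SDs beside a logMAR SD; both lean towards a log scale without fixing it. The group comparison that the plan names is unaffected by a linear change of unit.

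It is also fair to say that a larger mean IOD does not by itself show better detection: if control IODs or noise grow as much, nothing is gained. That bears on the remedy.

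**Conclusion.** The point holds as a failure to specify. The stated group comparisons cannot decide Hypothesis 1, because selection makes them nearly certain to be significant: about 96% for a 0.1 logMAR deficit at SD 0.1, and 99.8% in the simulation with no gain at all. This is more than missing detail, since the comparison the plan attaches to the hypothesis would mislead if used. The right contrast is feasible with the planned 42 amblyopes. Its precision rests on assumptions, because the documents give neither the SD of the contrast nor the correlation between measures. The scale question is conditional and disappears once all tests are analysed as log ratios.

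**What to change.** In the statistical section, state the following.

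- For each child and test, IOD = log10 threshold of the amblyopic eye minus that of the fellow eye. Crowding distance is analysed as log10 spacing, so that its IOD is a unit-free ratio comparable with logMAR.
- Which Crowding Distance measure, trigram or repeated numbers, is used for Hypothesis 1.
- The Hypothesis 1 test is the mean of IOD(new) minus IOD(SLT) within the 42 amblyopic children (the eye-by-test contrast), with subtype as a factor, a 95% confidence interval, and a multiplicity adjustment over the three new tests.
- The same contrast is reported in controls, using right and left eyes, so that a larger IOD can be judged against normal variation.
- Group comparisons of thresholds are supportive and do not decide Hypothesis 1.

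The Hypothesis 1 sample size should be restated in terms of the SD of this contrast, with its assumptions. The cost is wording only: each eye is already tested on each new test, and each eye's SLT result is already recorded.
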